5.1.3 Medical history date of diagnosis imputation

Completely missing dates and partially missing end dates will not be imputed. Partial dates of diagnosis will be compared to the treatment start date.

- If DIAG year < study treatment start date year and DIAG month is missing, the imputed DIAG date is set to the mid-year point (01JULYYYY).
- Else if DIAG month is not missing, the imputed DIAG date is set to the mid-month point (15MONYYYY).
- If DIAG year = study treatment start date year and (DIAG month is missing OR DIAG month is equal to study treatment start month), the imputed DIAG date is set to one day before study treatment start date.

5.1.4 Concomitant medication date imputation

Concomitant medication (CMD) start date imputation (#IMPUTMED)

Rules for imputing the CMD start date:

This algorithm is used when *event* is the partial start date of the concomitant medication, non- drug therapy/procedure, or prior study indication therapy.

The following table explains the notation used in the logic matrix. Please note that completely missing start dates will not be imputed.

	Day	Month	Year
Partial CM Start Date	Not used	MON	YYYY
Treatment Start Date (TRTSDT)	Not used	TRTM	TRY

The following matrix explains the logic behind the	MON MISSING	MON<TRTM	MON=TRTM	MON>TRTM
YYYY	(C2) Uncertain	(C1) Uncertain	(C1) Uncertain	(C1) Uncertain

MISSING				
YYYY<TRTY	(D) Before Treatment Start	(A) Before Treatment Start	(A) Before Treatment Start	(A) Before Treatment Start
YYYY=TRTY	(C2) Uncertain	(A) Before Treatment Start	(C1) Uncertain	(B) After Treatment Start
YYYY>TRTY	(E) After Treatment Start	(B) After Treatment Start	(B) After Treatment Start	(B) After Treatment Start

The following table is the legend to the logic matrix.

Relationship	
Before Treatment Start	Partial date indicates CMD start date prior to Treatment Start Date
After Treatment Start	Partial date indicates CMD start date after Treatment Start Date
Uncertain	Partial date insufficient to determine relationship of CMD start date relative to Treatment Start Date
Imputation Calculation	
(A)	15MONYYYY
(B)	01MONYYYY
(C1 or C2)	IF relative reference start = before treatment start THEN TRTSDT-1 ELSE IF relative reference start = ' ' THEN TRTSDT+1
(D)	01JULYYYY
(E)	01JANYYYY

Concomitant medication end date imputation

If not ongoing then –

- If the CM end date year value is missing, the date uncertainty is too high to impute a rational date. Therefore, if the CM end year value is missing or ongoing, the imputed CM end date is set to NULL.
- Else, if the CM end date month is missing, the imputed end date should be set to the earliest of the following options: treatment follow up period date, 31DECYYYY, date of death.
- If the CM end date day is missing, the imputed end date should be set to the earliest of the following: treatment follow up period date, last day of the month, date of death.
- If the imputed CM end date is less than the existing CM start date, use the CM start date as the imputed CM end date.

Concomitant medication date flag

If not a complete date then

Y - If year of the imputed date is not equal to YYYY else

M – If month of the imputed date is not equal to MON

else D

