2.4.2 Prior, concomitant and post therapies

Prior and concomitant therapies

Prior and concomitant medications will be summarized in separate tables by treatment group.

Prior medications are defined as treatments taken and stopped prior to first dose of study treatment. Any medication given at least once between the day of first dose of randomized study treatment and the date of the last study visit will be a concomitant medication, including those, which were started pre-baseline and continued into the period where study treatment is administered.

Medications will be presented in alphabetical order, by Anatomical Therapeutic Classification (ATC) codes and grouped by anatomical main group. Tables will show the overall number and percentage of patients receiving at least one treatment of a particular ATC code and at least one treatment in a particular anatomical main group.

Significant prior and concomitant surgeries and procedures will be summarized by primary system organ class and MedDRA preferred term.

The number and percentage of patients receiving prior and concomitant PsA therapy will be presented by randomized treatment group as well as the reasons for stopping their therapies (primary lack of efficacy, secondary lack of efficacy, lack of tolerability, other) and the total duration of exposure to PsA therapies previously.

In addition to that, summary of doses will also be performed for NSAID, MTX and corticosteroids. Comparison of median dose with ASAS recommendations will also be summarized.

Prior or concomitant medication will be identified by comparing recorded or imputed start and end dates of medication taken to the reference start date.

Rescue medication

Rescue medication is defined as medication used to control symptoms that are not adequately controlled on study treatment.

No patient will be restricted from receiving necessary rescue medications for lack of benefit or worsening of disease, if rescue with prohibited treatments occurs prior to completion of Week 52 assessments, patients can be discontinued from the study treatment (as per the CTT's discretion) but can continue with the study visit assessments until at least Week 12.

Rescue medication will be summarized similarly to concomitant medication.

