5.7 Rule of exclusion criteria of analysis sets

Table 5-1 Protocol deviations that cause subjects to be excluded

Deviation ID	Description of Deviation	Exclusion in Analyses	Severity code
INCL01	Informed consent not obtained before study inclusion	EXCLUDE FROM FAS AND SAF	3
INCL02	Informed consent not signed or missing or date of signing ICF is missing.	EXCLUDE FROM FAS AND SAF	3
INCL03	BASDAI score is < 4 at baseline	EXCLUDE FROM FAS	1
INCL04	Spinal Pain VAS score is < 40 at Baseline	EXCLUDE FROM FAS	1
INCL05	No inadequate response to at least 2 NSAIDs over a period of 4 weeks	EXCLUDE FROM PPS	4
INCL06	Subject <18 years of age	EXCLUDE FROM FAS AND SAF	3
INCL07	Patient has no axial PsA diagnosis at screening	EXCLUDE FROM PPS	4
INCL08	CASPAR score is < 3 at screening	EXCLUDE FROM PPS	4
INCL09	Patient is a lactating woman	INCLUDE IN EVERYTHING	0
EXCL01	Evidence of ongoing infectious or malignant processes, obtained within 3 months prior to Screening by Chest X ray or MRI	INCLUDE IN EVERYTHING	0
EXCL02	Patient takes high potency opioid analgesics	EXCLUDE FROM PPS	4
EXCL03	History of exposure to other IL-17 or IL-23 inhibitor biologic drug(s)	EXCLUDE FROM PPS	4
EXCL04	History of exposure to previous biologic DMARD(s)	EXCLUDE FROM PPS	4

Deviation ID	Description of Deviation	Exclusion in Analyses	Severity code
EXCL05	Current treatment with DMARD(s) other than MTX at baseline	EXCLUDE FROM PPS	4
EXCL06	Any therapy by intra-articular injections within 4 weeks before randomization	EXCLUDE FROM PPS	4
EXCL07	Patient taking NSAIDs is not on a stable dose for at least 2 weeks before randomization.	EXCLUDE FROM PPS	4
EXCL08	Patient taking systemic corticosteroids is not on a stable dose \leq 10 mg/day of prednisone for at least 2 weeks before randomization.	EXCLUDE FROM PPS	4
EXCL09	Patients who are on MTX (\leq 25 mg/week) who are not on a stable dose for at least 4 weeks before randomization	EXCLUDE FROM PPS	4
EXCL10	Patients on MTX who are not on folic acid supplementation at randomization	INCLUDE IN EVERYTHING	0
EXCL11	Patients who are on DMARD(s) other than MTX and who have not discontinued the DMARD(s) 4 weeks before randomization (8 weeks for leflunomide unless cholestyramine washout has been performed)	EXCLUDE FROM PPS	4
EXCL12	Active ongoing inflammatory diseases other than psoriasis that might confound the evaluation of the benefit of secukinumab therapy	EXCLUDE FROM PPS	4
EXCL13	Positive pregnancy test result before randomization	INCLUDE IN EVERYTHING	0

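### The concomitant-medication date rules ignore the stop date when imputing a start, so with two partial dates and a blank flag a drug stopped before first dose is tabulated as concomitant

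*SAP*

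**What the plan says.** SAP section 5.1.4 states that its start-date algorithm covers concomitant medication, non-drug therapy and earlier therapy for the study indication. A matrix of start year and month against the treatment-start year and month leads to one of several imputations. The cells labelled uncertain (C1 and C2) are described as "Partial date insufficient to determine relationship of CMD start date relative to Treatment Start Date". They apply when:

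- the start year is missing;
- the start year equals the treatment year and the month is missing; or
- the start year and month both equal those of first dose.

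The imputation in these cells is "IF relative reference start = before treatment start THEN TRTSDT-1 ELSE IF relative reference start = ' ' THEN TRTSDT+1".

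For stop dates, the section says "If the CM end date day is missing, the imputed end date should be set to the earliest of the following", and the candidates listed are the follow-up date, the end of that month and the date of death. The last rule settles any conflict of order: "If the imputed CM end date is less than the existing CM start date, use the CM start date as the imputed CM end date".

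Section 2.4.2 defines prior medication as medication stopped before first dose and concomitant medication as anything given at least once from first dose to the last study visit. It then says "Prior or concomitant medication will be identified by comparing recorded or imputed start and end dates of medication taken to the reference start date". It also plans a summary of how long patients were previously exposed to PsA therapies.

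On completely missing starts, section 5.1.4 says "Please note that completely missing start dates will not be imputed". Section 5.1.4.1, on date imputation for prior therapies, is marked not applicable.

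**The concern.** A reported stop month is real information. In the uncertain cells the plan sets it aside and places the start next to first dose on the strength of a flag alone. If the result contradicts the stop, the plan moves the stop, which rests on a recorded month, to match the start, which does not. A drug that the record itself shows was stopped before dosing can then be counted as taken on study. Where it is not, its stop date or its duration can still be wrong.

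At stake are the prior and concomitant medication tables and the duration of earlier PsA therapy. These describe the population and its background treatment, and on-study disease-modifying drug use is a line that readers will look at.

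The section also leaves two points on which two programmers could differ: whether a start with neither year nor month is imputed, and whether prior PsA therapy falls under the algorithm at all.

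**Working it through.** The plan gives no figure to reproduce, so the check is to run the rules as written on example dates. The first-dose dates below are assumptions for illustration.

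**Inputs.** From section 5.1.4: the C1/C2 rule, the stop-date rule and the order-conflict rule. From section 2.4.2: classification on recorded or imputed dates. From section 2.1.1: first dose is Day 1, the day before is Day -1, and there is no Day 0. *Existing* start date in the conflict rule is read to include an imputed start.

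**Case 1: first dose 1 Jun 2018, start recorded as 2018, stop recorded as Mar 2018.**

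1. Start cell: year equals treatment year, month missing, so C2.
2. Stop: day missing, so 31 Mar 2018. Distance to first dose = 30 (April) + 31 (May) + 1 = 62 days.
3. Flag blank: start = first dose + 1 = 2 Jun (Day 2). The stop of 31 Mar is earlier than 2 Jun, so it is moved to 2 Jun. Class: concomitant.
4. Flag *before*: start = first dose - 1 = 31 May (Day -1). The stop is moved to 31 May. Class: prior, but the stop is 30 + 31 = 61 days later than the end of the recorded month.

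**Case 2: as case 1, but stop fully recorded as 15 Mar 2018.** The conflict rule concerns imputed stops only, so the stop stays. Flag blank: the start of 2 Jun is 16 + 30 + 31 + 2 = 79 days after the stop. Flag *before*: the start of 31 May is 16 + 30 + 31 = 77 days after it. No rule resolves this. The drug can still be classed as prior from its stop date, but the duration is negative.

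**Further cases, first dose 16 Oct 2017:**

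| Start recorded | Stop recorded | Stop before conflict rule | Final stop, flag blank | Final stop, flag *before* |
|---|---|---|---|---|
| 2017 | Mar 2017 | 31 Mar 2017, Day -199 | Day 2, concomitant | Day -1, prior |
| May, no year | 2015 | 31 Dec 2015, Day -655 | Day 2, concomitant | Day -1, prior |
| 2017 | 20 Mar 2017 | unchanged, Day -210 | Day -210, prior, start after stop | Day -210, prior, start after stop |
| 2016 | Mar 2016 | 31 Mar 2016, Day -564 | 1 Jul 2016, Day -472, prior | 1 Jul 2016, Day -472, prior |
| Mar 2017 | 5 Mar 2017 | unchanged, Day -225 | Day -225, prior, start (15 Mar) after stop | Day -225, prior, start (15 Mar) after stop |

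The last two rows lie outside C1/C2. There the mid-year or mid-month start can also pass the stop; the class stays right but the dates do not.

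**With a cap at the stop.** Case 1: start = min(2 Jun or 31 May, 31 Mar) = 31 Mar, and stop = 31 Mar. The drug is prior whatever the flag. Counted inclusively, duration is 31 Mar - 31 Mar + 1 = 1 day. This is no longer negative or misplaced, but it is not the true duration.

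**Completely missing start.** The text says it is not imputed. The matrix cell with year and month both missing says C2, which imputes it. Both cannot be followed.

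**The case against.** The strongest reply is that misclassification needs four things together: a start month missing in the treatment year (or a missing start year), a partial stop date, a blank flag, and *existing* start date read to include imputed starts. This stands, and it limits the point. With the flag set to *before*, the class is correct. With a complete stop date, the stop does not move. If *existing* means recorded only, the stop is not moved, but the record keeps a start later than its stop, which is also unusable. The missing-year group is smaller still if the sentence on completely missing starts prevails; what remains is a month without a year.

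A reader might infer more: that patients would falsely fail washout criteria such as "Patients who are on DMARD(s) other than MTX and who have not discontinued the DMARD(s) 4 weeks before randomization", that on-study disease-modifying drug deviations would be wrongly raised, or that the methotrexate factor in the primary model would be miscoded. The SAP does not support this. Section 2.3.1 says that deviation dates lie outside the clinical database and are supplied by the clinical team. The washout and on-study disease-modifying drug deviations in section 5.7 (EXCL11, COMD02, COMD08) remove patients from the per-protocol set only, while the primary, key secondary and secondary efficacy analyses use the full analysis set. Nothing derives methotrexate status from imputed dates.

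It can also be said that section 5.1.4.1 takes prior therapies out of scope. It may, but section 5.1.4 expressly names prior study indication therapy, so the two have to be reconciled.

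**Conclusion.** The point holds as a limited one. Applied literally, section 5.1.4 can date a drug with a known pre-dose stop month to Day 2, and section 2.4.2 then counts it as concomitant, contrary to its own definition. In the illustrative case a stop 62 days before first dose becomes Day 2 (flag blank) or Day -1 (flag *before*); with a stop recorded as 15 Mar, the start falls 77 or 79 days after it.

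This rests on reading *existing* start date as including imputed starts, and on a blank flag for the misclassification. How the flag is filled, and how many records have such dates, cannot be told from the SAP. The effect is confined to descriptive prior and concomitant medication tables and prior PsA therapy durations. No effect on the primary analysis, the methotrexate factor or the deviation flags is shown.

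**What to change.** In section 5.1.4:

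1. Impute the stop date first.
2. Cap any imputed start, in every cell of the matrix, at the recorded or imputed stop date.
3. Apply the rule that moves the stop to the start only when the start is fully recorded.
4. Class as prior any medication whose recorded stop month and year (or stop year alone) precede those of first dose, whatever the flag.
5. Change the cell with year and month both missing from C2 to not imputed, to match the text.
6. Reconcile the stated coverage of prior study indication therapy with section 5.1.4.1.

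The cap removes negative durations and misplaced stop dates but does not recover the true length of therapy. Durations that rest on a capped start should therefore be set to missing or flagged in the prior PsA therapy summary.

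The cost is a few lines of SAP text and programming. No new data are needed.

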5.1.4.1 Prior therapies date imputation

Not applicable

5.1.4.2 Post therapies date imputation

Not applicable

5.2 AEs coding/grading

The verbatim term recorded on CRF will be identified as adverse event and will be coded by primary system organ class and preferred term using Medical Dictionary for Regulatory Activities (MedDRA) version 18.1 and above.

5.3 Laboratory parameters derivations

Refer to main section of SAP.

5.4 Statistical methodology and assumptions

5.4.1 Crude incidence and 100*(1- α) % confidence interval

For n subjects, each at risk to experience a certain event with probability π , the crude incidence is estimated as $p=x/n$, where x is the number of subjects with the event.

Absolute and relative frequencies will be displayed as well as 95% confidence interval for the relative frequency based on the score method including continuity correction (Newcombe 1998).

With z as $(1-\alpha/2)$ -quantile of the standard normal distribution (SAS: $z=PROBIT(1-\alpha/2)$), n as total number of subjects (i.e. number of subjects in the denominator), and p as estimated crude incidence (number of subjects with event / n) it is $q=1-p$.

Then the lower limit is

$$L = \max\left(0, \frac{2np + z^2 - 1 - z\sqrt{z^2 + 2 - \frac{1}{n} + 4p(nq+1)}}{2(n+z^2)}\right)$$

and the upper limit is

$$U = \min\left(1, \frac{2np + z^2 + 1 + z\sqrt{z^2 + 2 - \frac{1}{n} + 4p(nq-1)}}{2(n+z^2)}\right).$$

Note: if $p = 0$ then $L = 0$ and if $p = 1$ then $U = 1$.

If appropriate, an exact $100*(1-\alpha)\%$ confidence interval (Clopper-Pearson 1934) will be obtained by using the SAS procedure PROC FREQ with the EXACT BINOMIAL statement. However, the confidence interval derived via the score method including continuity correction will be the default in safety analyses.

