2.8.4 Other safety data

2.8.4.1 ECG and cardiac imaging data

The following quantitative variables will be summarized: RR interval, PR interval, QRS duration, QT interval, and Fridericia (QTcF) correction will be presented for QTc.

QTcF will summarized by computing the number and percentage of patients (including 95% confidence intervals for pooled analyses, e.g. DMC or SCS) with:

- QTcF > 500 msec
- QTcF > 480 msec
- QTcF > 450 msec
- QTcF changes from baseline > 30 msec
- QTcF changes from baseline > 60 msec
- PR > 250 msec

Summary statistics will be presented for ECG variables by visit and treatment group.

In addition, shift tables comparing baseline ECG interpretation (normal, abnormal, not available, total) with the worst on-study interpretation (normal, abnormal, not available, total) will be provided.

A listing of all newly occurring or worsening abnormalities will be provided, as well as a by subject listing of all quantitative ECG parameters.

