5.6.1 Secondary analyses

Categorical variables will be analyses using the logistic model, code is described above.

Endpoints with continuous data type expected to be normally distributed will be analyzed using an analysis of covariance (ANCOVA) model with treatment and baseline stratification factor, and baseline value as covariate. Confidence intervals for the difference between each dose of secukinumab and placebo will be calculated.

SAS code for ANCOVA

```
proc mixed data=aaa;
class TRT STRATA;
model response = TRT STRATA BASE / s;
lsmeans TRT / diff;
run;
```

In addition, key secondary variables measured at all post baseline visits up to Week 52 will be analyzed using longitudinal mixed effects ANCOVA model with treatment, baseline stratification factor and analysis visit as factors; and weight, baseline value, treatment by visit and baseline by visit interactions as covariates. An unstructured covariance structure will be assumed for this model. The significance of the treatment effects for secukinumab regimens at different analysis visits will be determined from the pairwise comparisons performed between secukinumab regimens and placebo at the appropriate analysis visits.

SAS code for mixed model:

```
proc mixed data=aaa;
class TRT USUBJID AVISITN STRATA;
model CHG=TRT STRATA AVISITN WEIGHT BASE TRT*AVISITN BASE*AVISITN
/ s ddfm=kr;
lsmeans TRT*AVISITN / diff cl;
repeated AVISITN / type=un subject=USUBJID;
Run;
```

In case the MMRM model does not converge the following sequential steps will be used:

1. change ddfm=kr to ddfm=bw. If still no convergence, perform step 2.
2. change type=un to type=cs. If still no convergence, perform step 3.

3. remove covariates in the following order until convergence: WEIGHT, BASE*AVISITN, STRATA.

Crude and adjusted incidence rates

The SAS codes of crude and adjusted incidence rates and confidence intervals will be referred from the MAP or AIN457F2310 M3.

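### Low severity: the lower limit in section 5.4.1 has the wrong sign under the root, so it is not the continuity-corrected score limit the SAP names as the safety default

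*SAP*

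**What the plan says.** SAP section 5.4.1 estimates the crude incidence as p = x/n, sets q = 1 - p, and plans to display absolute and relative frequencies with a "95% confidence interval for the relative frequency based on the score method including continuity correction". It makes this interval the safety default ("the confidence interval derived via the score method including continuity correction will be the default in safety analyses") and allows an exact Clopper-Pearson interval where appropriate.

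Both limits are then written out, with z the (1 - alpha/2) normal quantile. As supplied:

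- `L = max(0, [2np + z^2 - 1 - z*sqrt(z^2 + 2 - 1/n + 4p(nq+1))] / [2(n+z^2)])`
- `U = min(1, [2np + z^2 + 1 + z*sqrt(z^2 + 2 - 1/n + 4p(nq-1))] / [2(n+z^2)])`

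A note sets L = 0 when p = 0 and U = 1 when p = 1.

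Two other places bear on use. Section 5.6.1 (Secondary analyses) states: "The SAS codes of crude and adjusted incidence rates and confidence intervals will be referred from the MAP or AIN457F2310 M3". Section 2.8.4.1 asks for the number and percentage of patients over QTcF thresholds, "including 95% confidence intervals for pooled analyses, e.g. DMC or SCS".

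**The concern.** Between L and U the sign of the 1 outside the root changes, and so does the sign inside the bracket (nq+1 against nq-1). The sign of the 2 does not. A two-sided score interval must give the same answer whether events or non-events are counted, so the two limits should be mirror images. With + 2 in both, they are not.

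At stake is agreement between a formula stated as a default and the method it is said to implement. A programmer who codes L as printed gets lower limits that are too low, most visibly for rare events. One who validates correct code against the SAP finds a mismatch with no explanation.

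**Working it through.** **Inputs.** z = 1.95996 (two-sided 5%). n = 165, the planned recruitment per group in SAP section 3, used for illustration; n = 330 is two such groups. The formulas are those of section 5.4.1. The SAP gives no worked example of this interval, so there is no printed figure to reproduce.

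**Check 1: mirror the SAP's own U.** Replace p by q in U and subtract from 1. The numerator of 1 - U(n-x) is

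`2(n+z^2) - [2nq + z^2 + 1 + z*sqrt(z^2 + 2 - 1/n + 4q(np-1))]`
`= 2np + z^2 - 1 - z*sqrt(z^2 + 2 - 1/n + 4q(np-1))`.

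Since `4q(np-1) = 4npq - 4q = 4npq + 4p - 4 = 4p(nq+1) - 4`, the expression under the root is `z^2 - 2 - 1/n + 4p(nq+1)`. The rest equals the printed L; only the sign of the 2 differs.

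**Check 2: solve the method directly.** The lower limit t satisfies `(p - t) - 1/(2n) = z*sqrt(t(1-t)/n)`. With `c = p - 1/(2n)`, squaring gives `t^2(n+z^2) - t(2nc+z^2) + nc^2 = 0`. Its discriminant is `z^2[z^2 + 4nc(1-c)]`, and `4nc(1-c) = 4p(nq+1) - 2 - 1/n`. The expression under the root is again `z^2 - 2 - 1/n + 4p(nq+1)`.

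**Numbers for n = 165, x = 3.** p = 0.018182, nq = 162, 4p(nq+1) = 11.8545, 2(n+z^2) = 337.683.

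- Printed: 3.8415 + 2 - 0.0061 + 11.8545 = 17.6899. L = (8.8415 - 1.95996 × 4.2059) / 337.683 = 0.00177.
- With - 2: 13.6899. L = (8.8415 - 1.95996 × 3.7000) / 337.683 = 0.00471.
- Mirror, 1 - U(162): the value under the root is 3.8415 + 2 - 0.0061 + 7.8545 = 13.6899, so 1 - U = 0.00471, equal to the - 2 version.

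**Lower limit over a range of counts, n = 165.**

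| Events | L as printed | L with - 2 | Shortfall (points) |
|---|---|---|---|
| 1 | 0 | 0.03% | 0.03 |
| 2 | 0 | 0.21% | 0.21 |
| 3 | 0.18% | 0.47% | 0.29 |
| 5 | 0.88% | 1.12% | 0.24 |
| 10 | 2.93% | 3.11% | 0.18 |
| 82 | 41.78% | 41.87% | 0.09 |
| 165 | 96.75% | 97.16% | 0.42 |

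Shortfalls are taken before rounding. At 1 and 2 events the raw printed values are negative (-0.00387 and -0.00129) and are floored at 0. The largest shortfall is 0.29 points for events in up to half an arm, 0.34 points for x < n (at 164 events) and 0.42 points over all counts. The last arises at x = 165, where the boundary note fixes only U, so the L formula still applies. At n = 330 the maximum is 0.15 points up to half the group (3 events: 0.09% against 0.24%) and 0.21 points over all counts.

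**Agreement.** With - 2, L equals 1 - U(n-x) to within 1e-15 and the direct root to within 1e-12 for every x from 1 to n-1 at n = 165, 330 and 495. The printed L matches neither the plain Wilson nor the Clopper-Pearson limit. The printed U agrees with the direct solution for every x < n checked, and x = n is covered by the note.

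**The case against.** Four points can be made on the other side.

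1. *It may be a reading error.* The formula was extracted from a PDF by a program, and the two expressions under the roots are near twins. Without the page, a minus read as a plus cannot be excluded. This stands: the error is shown for the text as supplied. A reader might infer that the sponsor's own page is wrong; that has to be looked up.

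2. *The output need not come from this formula.* The SAP takes the code for crude rates and their intervals from another source, which is not shown. The code in section 5.6.1 (Primary analysis) already calls PROC FREQ's continuity-corrected Wilson option, though for response rates. This also stands. A reader might infer that the trial's safety tables will carry wrong limits; the document does not show that. It does not remove the point, because correct code would then disagree with the SAP's stated formula.

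3. *Few tables would show the interval.* Section 5.4.1 says it will be displayed, but section 2.8 asks explicitly for an interval on a crude percentage only for QTcF in pooled analyses. Its other intervals belong to exposure-adjusted rates (2.8.1) or time-to-event quartiles (2.8.1.1), and the safety overview table lists crude rates without intervals. This limits the reach.

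4. *The effect is small and conservative.* Correct. The printed L is never above the right one, so the interval only widens and coverage cannot fall. A reader might infer anti-conservative safety reporting or an effect on the trial's conclusions; neither follows.

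**Conclusion.** The point holds at low severity. As supplied, the lower limit in section 5.4.1 is not the continuity-corrected score limit named there, and the SAP's own upper limit is enough to prove it. Lower limits computed as printed would be too low by at most 0.29 percentage points for events in up to half an arm of 165, and by 0.42 points at the extreme of 165 events in 165 patients. In relative terms the effect is largest for rare events, where a positive limit can become 0.

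Point estimates, upper limits, the exposure-adjusted intervals of section 5.4.3, Kaplan-Meier estimates and all efficacy results are untouched. The conclusion assumes that the + 2 is on the original page. Any effect on output further assumes that the printed formula, or code with the same sign, is used. The sizes assume 165 patients per group; actual safety-set denominators will shift them slightly.

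**What to change.** Confirm the sign on the original page of section 5.4.1. If it is + 2, change it to - 2 under the root of L; leave U and the notes for p = 0 and p = 1 as they are.

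Check that the borrowed safety code satisfies L(x) = 1 - U(n-x) for a few counts from 1 to n-1. At n = 165 and x = 5 both sides should be 0.01121; the printed formula gives 0.00880. Alternatively, take both limits from PROC FREQ's continuity-corrected Wilson option.

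The cost is one sign in an appendix and one program check, with no statistical trade-off.
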